5.4.2 Continuous Data

Continuous data will be described by summary tables of sample characteristics by visit and for changes between visits as defined in Section 3.2.2 above. Selected continuous variables will be visualized by box plots by treatment group and visit.

ANCOVA

Comparisons will be done using an ANCOVA model including treatment, analysis site and baseline PGA as factors, and the baseline value of the respective endpoint as covariate.

The statistical model is

endpoint = $\beta_0 + \beta_1$ ·baseline value + treatment + analysis site + baseline PGA + error,

where β_1 is a parameter of fixed effect and β_0 an intercept. The estimated differences between MC2-01 cream MC2-01 cream vehicle, and between active comparator and MC2-01 cream vehicle, will be reported together with the associated standard error, the 95% confidence interval, and a p-value of a test on the respective contrast corresponding to the hypothesis as either no difference between treatments (superiority) or difference between treatments within the tolerance limits (non-inferiority) (cp. Section 5.2 above).

5.5 Application of Methods

Statistical hierarchical testing will be applied as described in Sections 5.2, 5.3 and 5.4.2. The following subsections describe the application of methods per endpoint, summarized in Section 5.5.5.

Multiple Imputation Procedure

Applicable to all endpoints with MI, the procedural steps are as follows. On 100 multiple complete imputed datasets as produced according to the instructions in Section 4.7.2, each dataset will be analyzed the same way. After pooling the estimates and standard errors, results will be aggregated following Rubin's rule to yield one estimate and associated standard error, and to calculate the 95% confidence interval for the

treatment difference or odds ratio between treatments, respectively [11]. In data listings, multiply imputed values are described by mean values.

5.5.1 Primary Efficacy Endpoint

The primary endpoint, percentage change in mPASI on the body (trunk and/or limbs) from baseline to Week 8, will be analysed for superiority and non-inferiority by means of ANCOVA as described in Section 5.4.2.

Primary Analysis

The primary analysis is for superiority of MC2-01 cream versus MC2-01 cream vehicle and of active comparator versus MC2-01 cream vehicle as well as for non-inferiority of MC2-01 cream and active comparator using the treatment-policy strategy on the FAS using MI to impute missing data. The estimated pairwise differences will be reported together with the associated standard error, the 95% confidence interval, and p-values of testing hypotheses H_{0a} , H_{0b} and H_{0c} .

Sensitivity Analyses

Three sensitivity analyses are planned on the primary endpoint, for internal validity a tipping-point analysis following the treatment-policy strategy on the FAS using MI, for external validity an analysis following the hypothetical strategy on the FAS using MI, and an analysis following the treatment-policy strategy on the PPS.

Tipping-point analysis for treatment-policy strategy on the FAS

The primary analysis of mPASI using MI assumes that data are missing at random (MAR) within each treatment arm. For each hypothesis, the sensitivity of the MAR assumption is investigated using a tipping-point analysis [10]. A penalty (a number) is added to all imputed Week 8 values in the MC2-01 cream treatment group or (when testing superiority of active comparator vs. vehicle) in the active comparator group, and the analysis is repeated on the FAS for the treatment-policy estimand as described for the primary analysis. The penalty is gradually increased until the point, the tipping point, where the conclusion (superiority or non-inferiority depending on the analysis) no longer is demonstrated. The tipping point will be reported. If the tipping point is considered a clinical plausible difference, the tipping-point analysis does not support the primary analysis.

Hypothetical strategy on the FAS

mPASI is analysed following the hypothetical strategy as described in Section 5.3 on the FAS using MI for missing and unused data as described in Section 4.7.2.

Treatment-policy strategy on the PPS

mPASI is analysed following the treatment-policy strategy as in the primary analysis, but on the PPS without using any imputation approach.

5.5.2 Secondary Efficacy Endpoints

If the primary analysis of the primary endpoint yields rejection of all hypotheses, hierarchical testing is continued on secondary efficacy endpoints, with PGA success at first, followed by PTCS.

PGA Success

The first and fourth secondary efficacy endpoints are the percentage of subjects with PGA success on the body and on the scalp at Week 8, respectively, as defined in Section 2.4.1.

Primary Analysis

Considering PGA as a continuous endpoint, missing data will be imputed using MI as described in Section 4.7.2. On derived PGA success following the treatment-policy strategy, hypotheses will be tested, and comparisons of treatment groups done using a model of logistic regression as described in Sections 5.2 and 5.4.1.

Sensitivity Analyses

Two sensitivity analyses are planned on the first secondary endpoint, an analysis following the treatmentpolicy strategy on the FAS using NRI, and an analysis following the hypothetical strategy on the FAS using MI. On PGA success, non-response is defined as no PGA success.

In a first sensitivity analysis, missing data will be imputed using NRI as described in Section 4.7.2. On PGA success following a treatment-policy strategy, hypotheses will be tested, and comparisons of treatment groups done using a model of logistic regression as described in Sections 5.2 and 5.4.1.

In a second sensitivity analysis, missing and unused data will be imputed using MI as described in Section 4.7.2. On PGA success following a hypothetical strategy, hypotheses will be tested, and comparisons of treatment groups done using a model of logistic regression as described in Sections 5.2 and 5.4.1.

PTCS

The second secondary efficacy endpoint is the PTCS total score at Week 8. The PTCS total score will be analysed by means of an analysis of variance with treatment, analysis site and baseline PGA as factors.

Analysis of PTCS is following a while-on-treatment strategy using data as described in Section 5.3. Missing and invalid data will be imputed using LOCF as described in Section 4.7.2.

Primary Analysis

The primary analysis of PTCS will be based on the FAS following the while-on-treatment approach using LOCF to impute missing and invalid data.

Sensitivity Analyses

A sensitivity analysis of PTCS will be based on the PPS following the while-on-treatment approach using LOCF to impute missing and invalid data.

mPASI 75

mPASI 75 at Week 8 will be analyzed on the FAS like PGA success at Week 8 including mPASI at baseline as a covariate.

5.5.3 Other Efficacy Endpoints

Efficacy and subject-related outcomes will be exploratorily analyzed on the FAS at Week 4 as described for Week 8 above, without formal statistical hypothesis testing.

PGA success at Week 4 and mPASI 75 at Week 4 will be analyzed on the FAS like PGA success at Week 8 including mPASI at baseline as a covariate (cp. Section 5.4.1).

Observed changes from baseline in SGA at Week 4 and Week 8, and changes from baseline in BSA involvement on the body and the scalp will be presented descriptively on the FAS.

DLQI domain and total scores will be summarized by visit including changes from baseline on the FAS. Changes from baseline in the DLQI total score at Week 4 and Week 8 will be analyzed on the FAS by means of ANCOVA as described in Section 5.4.2 utilizing MI. Imputations will be made on the domain level to derive the DLQI total score.

Observed EQ-5D dimension assessments and VAS score will be summarized by visit on the FAS. Changes from baseline in EQ-VAS score at Week 4 and Week 8 will be analyzed on the FAS by means of ANCOVA as described in Section 5.4.2 utilizing MI.

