8.0 STATISTICAL METHODS AND DETERMINATION OF SAMPLE SIZE STATISTICAL AND ANALYTICAL PLANS

8.1 General Considerations for Data Analysis

The methodology presented below represents a brief overview of the statistical methods that will be fully detailed in the statistical analysis plan (SAP). The SAP will be finalised before the database is locked. Any changes to the methods described in the final SAP will be described and justified in the clinical trial report. All statistical analyses will be performed using SAS® statistical software (Version 9.2 or higher). Statistical significance will be tested at the 2-sided 5% level unless otherwise specified.

Subjects will be randomised in a 3:1:3 ratio (MC2-01 cream: MC2-01 cream vehicle: active comparator), stratifying by trial site. The aim is to randomise 14 subjects or more at each site. Furthermore, on a country level, it will be ensured that up to 30 % of the population can be subjects with mild disease (based on the PGA performed at Baseline), as monitored by data management. It is planned that the data from trial sites that participate in this trial will be combined so that an adequate number of subjects will be available for analysis. Trial sites yielding fewer than 14 subjects overall will be combined in order of geographical proximity. The exact composition of these "analysis sites" will be determined and documented prior to breaking the trial blind. In statistical models, site will refer to trial site or analysis site, if combination of trial sites is needed.

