- The common standard deviation is assumed to be 38 (based on the assumption of an SD of 35 in the active treatment arms (see above Daivobet[®] Gel studies), 50 in the vehicle arm (found to be the largest SD in the above Daivobet[®] Gel studies), and the 3:1:3 ratio)
- The error probability is set to 0.05 for a 2-sided test

Under these assumptions, a sample size of N=204 per active treatment group for the non-inferiority evaluation, assuming 0 difference, results in a power of 88.9%. Thus, a total of 476 subjects should be randomised in a 3:1:3 ratio (MC2-01 cream: MC2-01 cream vehicle: active comparator).

MC2-01-C7

With 476 subjects randomised 3:1:3, and the assumption that the effect of both active treatments is -56 percentage points (the average effect found in the gel studies), and the effect of MC2-01 cream vehicle is -27 percentage points (the largest effect found for the ointment, found in the MCB-9905 INT study), the power for each of the superiority comparisons of MC2-01 cream and active comparator to MC2-01 cream vehicle with respect to mPASI is more than 99%. If 30% of subjects treated with either MC2-01 cream or active comparator respectively 11% of subjects treated with MC2-01 cream vehicle will have PGA success, the power for the each of the superiority comparisons with respect to PGA success is 90.4%.

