- mPASI: In analogy with the analysis of the primary endpoint, superiority of MC2-01 cream versus active comparator will be evaluated using an ANCOVA model including treatment, site, and baseline PGA as factors, and baseline mPASI as covariate. Missing mPASI values will be imputed using MI.
- PGA: Superiority of MC2-01 cream versus active comparator. PGA success will be compared between MC2-01 cream and active comparator using a logistic model with treatment, baseline PGA, and site as factors.

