8.6.3.1 Analysis of other endpoints

The statistical analyses of other endpoints will be exploratory only, and no formal statistical testing will be conducted.

Efficacy

The efficacy endpoints will be analyzed using the treatment-regimen policy estimand for the ITT population and imputing missing data using MI. For the dichotomous endpoints based on mPASI, values of mPASI will be imputed, and then dichotomized.

- Percentage change from baseline in mPASI at Week 4 will be analyzed like the primary endpoint including the same sensitivity analyses
- mPASI 75 at Week 4 and Week 8, and PGA success at Week 4 will be analyzed like PGA success at Week 8 (secondary endpoint), with the analyses of mPASI 75 including mPASI at baseline as a covariate.
- Change from baseline in SGA at Week 4 and Week 8, and change from baseline in PGA for the scalp at Week 4 and Week 8 will be presented descriptively only

Patient reported outcome

- The PCTS score at Week 4 will be analyzed like the PCTS score at Week 8
- The DLQI score as well as the scores for the individual domains (symptoms and feelings, daily activities, leisure, work and school, and personal relationship) will be summarized by trial visit and treatment group. Missing values, if any, will be incorporated based on the developers scoring instructions. Missing domains will be imputed using MI and then combined to a total score. Change from baseline in DLQI score at Week 4 and Week 8 will be analyzed for the treatment-regimen estimand and the ITT population using an ANCOVA model with treatment, site, baseline PGA, and baseline DLQI as factors

• For the EQ-5D VAS score as well as the 5 dimensions mobility, self-care, usual activities, pain/discomfort, and anxiety/depression, will be summarized by trial visit and treatment group. Change from baseline in EQ-VAS score at Week 4 and Week 8 will be analyzed for the treatment-regimen estimand and the ITT population imputing missing data using MI and using an ANCOVA model with treatment, site, baseline PGA, and baseline EQ-VAS as factors

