5.4.1 Categorical Data

Categorical data will be described by summary tables of counts and percentages. This includes zero counts of all possible categories, if any. Selected categorical variables will be visualized by bar charts by treatment group and visit.

Logistic Regression

Selected binary endpoints will be analysed using a logistic model with effects of treatment, analysis site, and the baseline value of the endpoint as factors. The estimated log odds ratios between the treatments at Week 8 will be derived together with the associated standard error and 95% confidence intervals.

Logistic regression is used for superiority testing only. The non-inferiority analysis is done without modelling by means of unadjusted risk differences between treatment groups. 95% confidence intervals will be computed using normal approximation.

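### Baseline mPASI is absent from the valid Week 8 PGA success models but, read literally, added at Week 4: a small optional improvement and one undeclared difference to reconcile

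*SAP*

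**What the plan says.** **Week 8, confirmatory.** For cream against gel, Protocol 8.6.2 states that "PGA success will be compared between MC2-01 cream and active comparator using a logistic model with treatment, baseline PGA, and site as factors". It gives the same three terms for the comparisons with vehicle, and the synopsis repeats them. SAP 5.4.1 specifies "a logistic model with effects of treatment, analysis site, and the baseline value of the endpoint as factors", which for PGA success means baseline PGA; SAP 4.3 also requires baseline PGA in every model. SAP 5.5.2 applies this model to PGA success at Week 8. Baseline mPASI appears in none of these places.

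**Week 4, exploratory.** SAP 5.5.3 says that "PGA success at Week 4 and mPASI 75 at Week 4 will be analyzed on the FAS like PGA success at Week 8". The same sentence then brings in baseline mPASI as a covariate and refers back to SAP 5.4.1, which has no mPASI term. Protocol 8.6.3.1 also treats Week 4 PGA success like Week 8, but "with the analyses of mPASI 75 including mPASI at baseline as a covariate", so there the covariate belongs to mPASI 75 alone.

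**Declared changes.** SAP 5.6 says that the protocol is followed and lists the endpoints that were promoted. It does not mention the Week 4 covariate.

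**Related models.** Baseline mPASI is in the ANCOVA for percentage change in mPASI and in the SAP 5.5.2 model for mPASI 75 at Week 8. The PGA imputation model in SAP 4.7.2 uses site, baseline PGA and earlier visits, without mPASI. SAP 5.4.1 limits logistic regression to superiority; non-inferiority on PGA success (step 6) is an unadjusted risk difference.

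**The concern.** Protocol 5.2 admits only mild or moderate disease on the body, so baseline PGA is in effect a two-level factor. Baseline mPASI is scored at Visit 1, is itself an entry criterion (at least 3), and grades extent as well as redness, thickness and scaliness in three regions. If it predicts PGA success beyond baseline PGA, leaving it out gives up some power at steps 4, 5 and 9.

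There is also a matter of consistency. Read literally, the SAP fits one endpoint with two covariate sets at two visits, and the Week 4 set departs from the protocol undeclared. The sentence can even be read as describing the Week 8 model, so two programmers could fit different models to a confirmatory test. Logistic odds ratios are conditional on the covariates, so the two visits' estimates would not be on exactly the same scale.

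**Working it through.** **1. Inputs from the documents**
- Level: "Statistical significance will be tested at the 2-sided 5% level unless otherwise specified" (Protocol 8.1).
- Size: "a total of 476 subjects should be randomised in a 3:1:3 ratio" and "a sample size of N=204 per active treatment group for the non-inferiority evaluation" (Protocol 8.2), so vehicle has 476 − 2 × 204 = 68.
- Rates: 30% in each active arm, and "11% of subjects treated with MC2-01 cream vehicle will have PGA success" (Protocol 8.2).
- Stated power for each PGA comparison with vehicle: 90.4%.

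**2. The plan's own figure (30% versus 11%, 204 versus 68)**
- Pooled rate = (0.11 × 68 + 0.30 × 204)/272 = 68.68/272 = 0.2525.
- SE under the null = √[0.2525 × 0.7475 × (1/68 + 1/204)] = 0.0608.
- SE under the alternative = √[0.11 × 0.89/68 + 0.30 × 0.70/204] = 0.0497.
- Power = Φ[(0.19 − 1.96 × 0.0608)/0.0497] = Φ(1.42) = 92.3%.

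Exact enumeration gives 92.4% for the chi-square test, 91.8% for Fisher and 89.1% with Yates' correction. The stated 90.4% is reproduced to within about 2 points.

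**3. Effect of adding baseline mPASI**

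The documents give no prognostic strength for baseline mPASI, so it is assumed as an odds ratio per SD, given baseline PGA. Simulation: 204/68/204, 34 sites of 14, site and baseline PGA as factors, 4,000 trials per setting. Further assumptions: 30% mild, correlation 0.3 between mPASI and PGA, log odds 0.5 for moderate versus mild, site SD 0.3, no missing data. Power (%) without → with mPASI:

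| Odds ratio per SD | Step 4 (30 v 11) | Step 5 (30 v 11) | Step 9 (assumed 42 v 30) | Median cream–vehicle odds ratio (30/11/30) |
|---|---|---|---|---|
| 1.0 | 93.4 → 93.4 | 93.5 → 93.4 | 74.4 → 74.2 | 3.94 → 3.95 |
| 0.8 | 93.1 → 93.4 | 93.3 → 93.6 | 74.5 → 74.3 | 3.90 → 3.94 |
| 0.67 | 93.1 → 93.1 | 93.5 → 93.8 | 73.6 → 74.7 | 3.89 → 4.03 |
| 0.5 | 93.1 → 94.3 | 93.6 → 94.9 | 74.1 → 77.4 | 3.86 → 4.32 |

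Monte Carlo error is about 0.4 points per rate at steps 4 and 5 (√(0.93 × 0.07/4000)) and 0.7 at step 9.

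**4. Other site structures and stronger covariates**
- 17 sites, odds ratios per SD of 0.74, 0.61 and 0.45: step 4 gains 0.1, 0.9 and 2.2 points. Step 9 goes 72.3 → 72.9%, 72.4 → 74.5% and 72.8 → 77.6%. With no prognostic effect, step 9 is 71.9% either way.
- 20 sites, mPASI correlated with baseline PGA, 0.74 to 0.45: gains of about 0.2 to 2.4 points at steps 4 and 5, and 1 to 5 points at step 9.

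**5. Step 9 under the planning assumption**

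At 30% in both active arms there is nothing to detect. In the 34-site runs the cream is declared better in 2.8 to 3.1% of trials without mPASI and 2.9 to 3.1% with it, so type I error is essentially unchanged.

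**6. Step 6**

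At 30% versus 30% with a 10-point margin, SE = √(2 × 0.3 × 0.7/204) = 0.0454 and power = Φ(0.10/0.0454 − 1.96) = 59.6%. No covariate enters this test, and step 9 is reached only if it succeeds.

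**7. Odds-ratio scale**

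From the last column, 3.95/3.94, 3.94/3.90 and 4.03/3.89 are shifts of 0 to 4%; 4.32/3.86 is 12%, at the strongest effect in that table.

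**The case against.** The best defence is that the Week 8 model is deliberate. The same terms stand in the synopsis, Protocol 8.6.2 and SAP 5.4.1, and they follow the principle in SAP 4.3: baseline PGA everywhere, plus the endpoint's own baseline. The odd text is the Week 4 sentence, which looks like a merger of PGA success with mPASI 75. On this view, three confirmatory tests should not be altered to match a slip in an exploratory analysis. Further, mPASI and PGA grade the same three signs, so the extra information may be modest; power against vehicle is already stated as 90.4%; and adding mPASI to the analysis model alone would leave the imputation model inconsistent with it.

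Most of this stands. It shows that the present model is sound, that the gain is small, and that any change must reach SAP 4.7.2. It does not show that the text can stay as it is, because Weeks 4 and 8 still differ undeclared. Nor does protocol prespecification bar the change: Protocol 8.1 leaves full detail to a SAP finalised before database lock, and SAP 5.6 already declares a change to the testing hierarchy.

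**Conclusion.** The point holds as a free improvement, in the sense that the covariate is already collected and no material power is lost if it proves uninformative. It is not an error in the plan. Expected gains are roughly 0 to 2.4 points at steps 4 and 5, and 0 to 5 points at step 9 if the cream is truly better (42% versus 30% is an assumption found nowhere in the documents). All gains rest on an assumed prognostic strength.

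Three stronger readings are tempting and are not supported:
- A reader might infer that the Week 8 analysis is deficient. It is the protocol's own model, and it adjusts for the endpoint's baseline.
- A reader might infer that substantial power is being thrown away. The documents give no prognostic strength, steps 4 and 5 are already at about 92%, and step 9 has no effect to detect under the planning assumption and lies behind the unadjusted step 6.
- A reader might infer that the Week 4 and Week 8 odds ratios cannot be compared. They are only not on exactly the same scale. Week 4 is exploratory, no comparison between visits is planned, and neither SAP Table 5 nor the table list in SAP 7.3 shows a modelled Week 4 PGA success analysis.

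The undeclared difference between SAP 5.5.3 and Protocol 8.6.3.1 is a plain fact and should be resolved either way.

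**What to change.** **Preferred, before unblinding.** Add baseline mPASI as a continuous covariate to the logistic model for PGA success on the body at Week 8 in SAP 5.4.1 and 5.5.2. This covers steps 4, 5 and 9 and their non-responder-imputation and hypothetical-strategy sensitivity analyses. Add it also to the PGA imputation model in SAP 4.7.2. List both changes, and the Week 4 covariate, in SAP 5.6.

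**Alternative.** If the sponsor keeps the protocol's Week 8 model, reword SAP 5.5.3 so that baseline mPASI applies to mPASI 75 only, as in Protocol 8.6.3.1. Weeks 4 and 8 then share one PGA model.

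**Cost.** The first option takes one term in two models and a few lines of SAP text, with no new data. It is a departure from Protocol 8.5 and 8.6.2, which is why it must be declared. The second is a one-sentence edit.

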5.5.4 Safety Endpoints

Safety endpoints will be described by summary tables on the safety set.

Treatment-emergent AEs, treatment-emergent drug-related AEs, treatment-emergent serious AEs (SAE), treatment-emergent drug-related SAEs, treatment-emergent AEs leading to drug withdrawal and treatment-emergent drug-related AEs leading to drug withdrawal will be presented in summary tables of the number and percentage of patients with at least one event, and the number of events, by primary SOC and by PT within SOC. For treatment-emergent AEs and treatment-emergent drug-related AEs, these summaries will also be provided by maximum severity. Maximum severity is defined by the most severe AE per subject, SOC and PT.

Local skin reaction sum scores, vital signs and laboratory parameters will be summarized by visit including changes from baseline. Frequencies of most intense local skin reactions will also be presented.

Using normal ranges, laboratory parameters will be presented in shift tables of frequencies of all categorized post-baseline versus categorized baseline values per visit (cp. Section 4.6.3).

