8.7.3 Other safety variables

Clinical laboratory values will be reported as complete listings of individual subject data. Laboratory parameters will include:

• Serum biochemistry: serum calcium (albumin corrected), serum albumin, serum alkaline phosphatase, serum phosphate, plasma parathyroid hormone. 25-OH Vitamin D (Assessed at Visit 1 and used to stratify patients and treatment effect on calcium metabolism).

• Urinalysis: urinary calcium, urinary phosphate, urinary calcium:creatinine ratio.

Clinical laboratory data will be summarised by presenting shift tables using extended normal ranges (baseline to most extreme post-baseline value), by presenting summary statistics of raw

data and change from baseline values (means, medians, standard deviations, ranges), and by the flagging of notable values in data listings.

Data from other tests (e.g., vital signs) will be considered as appropriate and listed. Notable values will be flagged, and any other information collected will be listed as appropriate. Any statistical tests performed to explore the data will be used only to highlight any interesting comparisons that may warrant further consideration.

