4.3 Subgroups and Confounding Factors for Analysis

No subgroup analysis will be done.

The potential confounding by trial sites will be considered by adjustment in statistical models. By country, trial sites with less than 14 FAS subjects will be pooled to form *analysis sites*. For trial sites with 14 FAS subjects or more, the trial site will be the analysis site.

The potential confounding by PGA at baseline will be considered by adjustment in all statistical models.

Depending on the endpoint as described below, the analysis may be adjusted by further confounding factors, particularly the baseline values of the respective endpoints in the models as covariates.

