4.6.2 Analysis Visit Windowing

Post-baseline visits are to be held at Weeks 1, 2, 4, 6, 8 and 10, namely at study Day 7, 14, 28, 42, 56 and 70, within two days from target day. In addition, unscheduled visits and visits of Early Termination may be given. Comprehensive non-overlapping visit windows are defined for Week 4 from Day 14 to Day 42 and for Week 8 as Day 43 or later, respectively, excluding any follow-up visits.

Primary and secondary efficacy endpoints will be summarized and analysed by *analysis visits*. For Week 4 and Week 8, analysis visits are defined as the visits held closest to the target day per analysis visit window as defined above. Any other visits within the same visit window will not be considered for analysis of primary or secondary efficacy endpoints. If the time distances of two visits from the target day are identical, the later visit is selected for analysis.

Other efficacy endpoints and safety endpoints will be summarized and analysed by nominal visits as appropriate.

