14.2.3	Other Efficacy Endpoints and Subject-Reported Outcomes
Table 14.2.3.1	%Change in mPASI Score at Week 4 – Analysis on the FAS using MI, Treatment-policy Strategy
Table 14.2.3.2	mPASI 75 at Week 4 – Analysis on the FAS using MI, Treatment-policy Strategy
Table 14.2.3.3	SGA – Summary by Visit on the FAS, Observed Cases
Table 14.2.3.4	PTCS Total Score at Week 4 –Analysis on the FAS using LOCF, While-on-treatment Strategy
Table 14.2.3.5	DLQI – Summary by Visit on the FAS, Observed Cases

Table 14.2.3.6	DLQI Score – Summary by Visit on the FAS, Averaged Multiple Imputations, Treatment- policy Strategy
Table 14.2.3.7	DLQI Score at Week 4 and Week 8 – Analysis on the FAS using MI, Treatment-policy Strategy
Table 14.2.3.8	EQ-5D – Summary by Visit on the FAS, Observed Cases
Table 14.2.3.9	EQ-VAS at Week 4 and Week 8 – Analysis on the FAS using MI, Treatment-policy
	Strategy DSA Inviction the Dody and the Seeln Summer by Visit on the EAS. Observed
Table 14.2.3.10	BSA Involvementon the Body and the Scalp – Summary by Visit on the FAS, Observed Cases
14.3	Safety Data
14.3.1	Adverse Events
Table 14.3.1.1	Adverse Events - Overview on the Safety Set
Table 14.3.1.2	Treatment-emergent Adverse Events - Summary by SOC and PT on the Safety Set
Table 14.3.1.3	Treatment-emergent Adverse Events – Summary by Maximum Severity, SOC and PT on the Safety Set
Table 14.3.1.4	Treatment-emergent Drug-related Adverse Events – Summary by SOC and PT on the Safety Set
Table 14.3.1.5	Treatment-emergent Drug-related Adverse Events – Summary by Maximum Severity, SOC and PT on the Safety Set
Table 14.3.1.6	Treatment-emergent Serious Adverse Events - Summary by SOC and PT on the Safety Set
Table 14.3.1.7	Treatment-emergent Drug-related Serious Adverse Events – Summary by SOC and PT on the Safety Set
Table 14.3.1.8	Treatment-emergent Adverse Events Leading to Drug Withdrawal – Summary by SOC and PT on the Safety Set
Table 14.3.1.9	Treatment-emergent Drug-related Adverse Events Located in the Treatment Area – Summary by SOC and PT on the Safety Set
14.3.2	Local Skin Reaction
Table 14.3.2.1	Local Skin Reaction Assessments - Summary by Visit on the Safety Set
Table 14.3.2.2	Most Intense Local Skin Reaction Assessments - Summary on the Safety Set
14.3.3	Laboratory Parameters
Table 14.3.3.1.1	Serum Biochemistry – Summary by Visit on the Safety Set
Table 14.3.3.1.2	Serum Biochemistry - Shifts from Baseline by Visit on the Safety Set
Table 14.3.3.2.1	Urinalysis – Summary by Visit on the Safety Set

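### The SAP replaces the protocol's worst-value laboratory shift with by-visit shifts and omits the vitamin D stratification, and declares neither change

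*SAP*

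**What the plan says.** Protocol 8.7.3 (Other safety variables) sets laboratory shift tables that run from "baseline to most extreme post-baseline value" and use extended normal ranges, a term it does not define. In its list of parameters it adds that 25-OH vitamin D is "Assessed at Visit 1 and used to stratify patients and treatment effect on calcium metabolism".

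SAP 5.5.4 (Safety Endpoints) plans "shift tables of frequencies of all categorized post-baseline versus categorized baseline values per visit", using the normal ranges of SAP 4.6.3 (low, normal, high). The table list in SAP 7.3 (Table 6) matches this: the serum entry reads "Serum Biochemistry - Shifts from Baseline by Visit on the Safety Set", with a parallel entry for urinalysis. No worst-value table is listed. SAP 4.6.2 says that "safety endpoints will be summarized and analysed by nominal visits as appropriate".

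SAP 2.4.2 keeps vitamin D as a Week 0 measurement, but no later section uses it to stratify anything. SAP 4.3 states: "No subgroup analysis will be done".

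SAP 5.6 (Changes and Clarifications) opens by saying that the analyses follow the protocol. Its only laboratory item is that notable laboratory ranges will not be defined.

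**The concern.** A reader who relies on SAP 5.6 would believe that both protocol analyses are still planned, when neither is. Safety is the trial's secondary objective. Protocol 8.7 bases the safety assessment mainly on adverse events, laboratory values outside predetermined ranges, and local skin reactions. Protocol 7.10.6 names raised serum calcium as a possible effect of excessive use of the cream.

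The SAP keeps a per-subject worst-case summary in the other two domains: adverse events by maximum severity, and most intense local skin reactions. Only laboratory data lose it, and no reason is given. At stake are a per-subject count of who was ever out of range, a defined place for off-schedule values, and the only analytic use that the protocol gives to the vitamin D measurement.

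**Working it through.** The documents state no figure for laboratory elevations, so there is nothing to reproduce. The check is a comparison of texts and one bound.

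**1. The texts side by side**

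| Item | Protocol 8.7.3 | SAP |
|---|---|---|
| Basis of the shift | Most extreme post-baseline value, one per subject | Each visit separately (5.5.4, Table 6) |
| Ranges | Extended normal ranges, undefined | Ordinary normal ranges (4.6.3, 5.5.4) |
| Baseline vitamin D | Stratifies patients and the effect on calcium metabolism | Measured (2.4.2), no stratified output; subgroups excluded (4.3) |
| Declared in SAP 5.6 | – | Notable laboratory ranges dropped; nothing on the worst-value basis or on vitamin D |

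**2. What by-visit tables can and cannot give**

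The scheduled on-treatment laboratory visits after baseline are Weeks 4 and 8 (Protocol Table 7-1, SAP 2.4.2). Of n subjects, let a be high at Week 4 and b at Week 8. Both counts appear in the tables. The number ever high does not, because it depends on the overlap:

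- lower bound (full overlap): max(a, b)
- upper bound (no overlap): min(a + b, n)

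When a + b ≤ n, the ratio of the bounds is (a + b) / max(a, b) = 1 + min(a, b) / max(a, b), which is at most 2. It equals 2 when a = b. The per-subject count is therefore uncertain by up to a factor of two, whatever the rates are. A worst-value table gives it directly.

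**3. Off-schedule samples**

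Protocol Table 7-1 marks laboratory assessments at the Week 10 follow-up, and Protocol 7.7.1 allows repeat samples. SAP 2.4.2 names only Weeks 0, 4, 8 and early termination, and SAP 4.6.2 works by nominal visit. The tables therefore have no clear place for unscheduled or Week 10 values.

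The gap is narrow. Repeats under Protocol 7.7.1 follow a result that is already abnormal, and the calcium repeat in Protocol 7.12 follows a Week 8 value already above range. With three categories, a repeat that is higher still stays in the same category. What lacks a place is a value that is out of range only off schedule.

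**4. Other routes by which raised values are reported**

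- Protocol 7.7.1: after Visit 1, a new abnormality that the investigator judges clinically significant is reported as an adverse event.
- SAP 4.4.5 and 5.5.4: treatment-emergent adverse events are counted as subjects with at least one event, with no restriction to scheduled visits.
- SAP 5.4 and Table 8: all collected data are listed, including serum biochemistry and urinalysis by visit.

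The loss in the tables is thus confined to elevations that are not judged clinically significant.

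**5. Vitamin D**

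Omitting the stratification leaves no calcium value out of the tables. It removes a planned look at whether the effect on calcium metabolism differs by baseline vitamin D.

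**The case against.** A reader might infer that raised calcium values will go uncounted, or that a value found only at an unscheduled visit is lost. The documents do not support this. Scheduled high values are tabulated at their own visit, clinically significant ones from any sample are counted per subject as adverse events, and every value is listed. If few subjects are affected, someone could work out the number ever high from the listings.

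The other side has further fair points:

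- Protocol 8.1 calls its methods a brief overview to be detailed in the SAP.
- SAP 4.3 rules out subgroups openly, and SAP 5.6 discloses that notable laboratory ranges are dropped, so the SAP is not wholly silent on the area.
- The vitamin D text is a parenthesis with no cut-off, outcome or method, and randomisation is stratified by site only.
- The worst-value shift covers all laboratory parameters, not calcium alone.
- SAP 5.5.5 calls the safety analyses descriptive and exploratory, so no test, margin or stopping rule depends on this.

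These points limit the consequence but do not remove the conflict. Replacing a worst-value shift with by-visit shifts changes the analysis rather than adding detail to it. SAP 4.3 does not say that it cancels a use of vitamin D planned in the protocol. The sentence on notable ranges may be read as touching the choice of range, but it says nothing about the most extreme value. SAP 5.6 is where such changes belong, and it reports agreement with the protocol.

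**Conclusion.** The point holds as a minor, undeclared conflict between SAP and protocol in a domain that the protocol names as a main basis of the safety assessment. Two planned analyses are absent, and the ranges change from extended to ordinary.

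The loss is the number of subjects ever out of range (known only to within a factor of two at most from the by-visit tables), a clear place for values seen only off schedule, and the look at calcium metabolism by baseline vitamin D. The factor of two assumes two scheduled on-treatment visits after baseline and that the two counts together do not exceed the group size. No absolute number can be given, because the documents state no rate of elevation. Whether ordinary ranges flag more or fewer values than the extended ones cannot be settled while the extended ranges are undefined. The efficacy conclusions are unaffected.

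**What to change.** - In SAP 5.5.4 and Table 6, add a shift table from baseline to the most extreme post-baseline value for the serum and urine parameters. Include unscheduled, early-termination and follow-up samples. The by-visit tables can stay.
- State which normal ranges the shift tables use, and record in SAP 5.6 any departure from the protocol's extended ranges.
- Add a descriptive summary of change in albumin-corrected calcium and urinary calcium by baseline 25-OH vitamin D category. The documents give no cut-offs, so the categories must be fixed before unblinding.
- Reword SAP 4.3 so that the exclusion of subgroup analyses applies to efficacy only.
- If the vitamin D summary is not restored, declare and justify that in SAP 5.6.

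The cost is two or three descriptive tables from data already collected. Alpha, power and trial conduct are unaffected.
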